### **1.5 Sample Size Justification**

We have a target N of 60 smokers (n=20/treatment condition). In terms of race/ethnicity, we anticipate our sample will be reflective of cigarette smokers living in the greater New Brunswick, NJ area: We expect to enroll two participants weekly in order to meet our target N. Estimating that 50% of the sample will make quit attempt during the course of the study, our main outcome of interest, this is adequate to group differences with 95% confidence (CI: 0.38, 0.61).

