#### **B. Dependent Variables or Outcome Measures**

Our DVs of interest are as follows: (1) pre-treatment to one-month follow-up change in (1a) motivation to quit (i.e., motivation), (1b) readiness to quit, and (1c) confidence in quitting; (2) setting a quit date (yes/no); (3) making a cessation attempt (yes/no); (4) days of self-reported abstinence, and (5) achieving initial CO verified abstinence (yes/no).

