### **4.3 Subject Randomization**

We will use a block randomization procedure to allocate participants to one of three groups. Block randomization is a procedure in which participants are randomly allocated to interventions groups within blocks such that an equal number are assigned to each intervention. We will use the Sealed Envelope Ltd. 2017 application to

electronically develop a list of 60 allocation outcomes using a block randomization procedure with 3 intervention groups and block sizes of 3, 6, and 9. A research assistant will use this list to create envelopes for therapists to open (revealing allocation to intervention) after each participant provides informed consent and is deemed eligible to participate in the study.

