**6.0 Research Data Protection and Reporting**

**6.1 Data Management and Confidentiality**

**A.** Success of randomization will be checked via summary statistics of baseline demographic and psychosocial characteristics. Depending on the measurement scale of each variable, we will use either  $\chi^2$  or independent samples t-tests, corrected for unequal variances if indicated. Variables found to show significant baseline differences between groups will be included as covariates. Logistic regression analyses will be conducted to examine differences in dichotomous outcomes such as abstinence (yes/no), quit attempts (yes/no), and treatment seeking (yes/no). Because this is a small, pilot study, we will report effect sizes representing each of the two active interventions (MI and NRT sampling) as compared to the control intervention (referral only).

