**B. Provide a power analysis. (As applicable, e.g. quantitative research).**

N/A. This is a small, pilot study. We will use the data collected in this study to estimate effect sizes for a larger NIH grant application.

**C. Describe the steps that will be taken to secure the data (e.g., training, authorization of access, password protection, encryption, physical controls, certificates of confidentiality, and separation of identifiers and data) during storage, use, and transmission.** The link between participants to their study ID will be stored in a password-protected file, located within a password-protected database on an encrypted computer. Only select trained laboratory personnel will have access to the file. All computer files or printed data used for analysis also

will be de-identified. Consent forms and payment forms will be stored in a locked file cabinet separate from data in an office (of Division of Addiction Psychiatry, [name]) that is locked when not occupied. All research personnel will complete CITI Human Subjects Research training and pass the CITI quizzes.

Additionally, we will obtain a Certificate of Confidentiality from the NIH

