Official Title: Addressing Tobacco in Public Housing Residents

Identifiers: NCT03620708

Document Date: September 27, 2019

Statistical Analysis Plan

To assess for differences in outcomes between groups we will use chi-square for dichotomous outcomes and analysis of variance / analysis of covariance for continuous outcomes. We will consider covariates based on theoretical grounds (e.g., baseline cigarettes per day, baseline motivation to quit, financial disadvantage) and significant differences between groups at baseline. Significant results will be probed using Dunnett's method, whereby our comparison of interest was between the treatment conditions and control condition. We will further report effect size estimates (i.e., f for ANOVA; Cramer's V for chi-square) to help elucidate aspects of the pilot study that may be most beneficial. Data will also be examined based on the assumption of 'missing equals smoking' and carrying the last observation (i.e., baseline data) forward, as a relatively conservative means of handling data for the n=5 participants lost to follow-up. We will refer to additional analyses of imputed data as intent-to-treat (ITT) analyses.

Outcome 1: A self-described "serious" attempt to quit smoking cigarettes since the initial study appointment, measured by the "Quitting Preparation and Actions Questionnaire."

We will use chi-square analysis to examine differences in proportion of the participants randomized to receive the three intervention groups with respect to making a serious quit attempt between the initial appointment and the 1-month follow-up period.

Outcome 2: Self-reported contact with one of two treatment referrals provided at intervention since the time of the initial study appointment

We will use chi-square analysis to examine differences in proportion of the participants randomized to receive the three intervention groups with respect to seeking treatment at either the NJ QuitLine or a NJ Quitcenter (local tobacco dependence treatment clinic) between the initial appointment and the 1-month follow-up period.

Outcome 3: Self-reported cigarettes smoked per day

We will use Analysis of Covariance (ANCOVA) to examine differences in cigarettes smoked per day at the 1-month follow-up between participants randomized to the three intervention groups. Baseline cigarettes smoked per day and measures of motivation to quit will be included as covariates.

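### The stated analyses of the yes/no outcomes may not give the active-versus-control effect sizes that the pilot is meant to produce

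*Protocol*

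**What the plan says.** **Protocol, 6.1 A (version 03.15.2019).** "Logistic regression analyses will be conducted to examine differences in dichotomous outcomes such as abstinence (yes/no), quit attempts (yes/no), and treatment seeking (yes/no"). Variables that differ significantly at baseline become covariates. The same paragraph promises effect sizes for MI and for NRT sampling, each against referral only. It names no effect scale, no exact or penalised method, and no rule for an arm without events.

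**Protocol, 6.1 B.** The power-analysis item is answered "N/A. This is a small, pilot study", and the data are to provide effect-size estimates for a larger grant application.

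**Protocol, 1.5, 1.6 B and 4.3.** "We have a target N of 60 smokers (n=20/treatment condition"), allocated "such that an equal number are assigned to each intervention". The only event rate given for a yes/no outcome is for quit attempts: "Estimating that 50% of the sample will make quit attempt during the course of the study, our main outcome of interest". The outcome list includes "achieving initial CO verified abstinence (yes/no"), with no expected rate.

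**SAP (September 27, 2019).** Dichotomous outcomes are tested by chi-square, with Cramer's V as the effect size. Dunnett's method is used to probe significant results. Two dichotomous outcomes are listed: a serious quit attempt, and "Self-reported contact with one of two treatment referrals provided at intervention since the time of the initial study appointment". Logistic regression is not mentioned, and abstinence is not among the five outcomes.

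**The concern.** The pilot's product is a pair of estimates per outcome: MI versus control and NRT versus control. A planner of the next trial needs a direction, a size and an interval for each.

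The two documents offer different routes, and each can fall short. The SAP's route stays calculable with sparse data, but it summarises three arms in one unsigned number. The protocol's route does give arm-versus-control contrasts, but it can break down with about 20 per arm if the outcome is uncommon. When an arm has no events, the maximum-likelihood odds ratio involving it is zero, infinite or undefined. If control is the empty arm, both contrasts are lost. Adding covariates does not remove the problem.

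At stake is a pilot that ends with a Cramer's V that cannot be carried into a two-arm calculation, or with a very large odds ratio and no usable interval.

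**Working it through.** **Inputs.** 20 per arm and a 50% quit-attempt rate (Protocol 1.5); equal allocation (4.3); 5 lost to follow-up (SAP). No rate is given for abstinence or treatment seeking, so a range is assumed. If 60 were randomised (an assumption, since Protocol 4.5 also gives a total of 64), 55 remain, or about 18 per arm.

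**1. The plan's own figure.** Section 1.5 states: "this is adequate to group differences with 95% confidence (CI: 0.38, 0.61"). For 50% of 60, the Wald interval is 0.5 ± 1.96 × √(0.25/60) = 0.373 to 0.627. The Wilson interval is 0.377 to 0.623. The closest match is Wilson, with the upper limit off by 0.01. Either way it describes one pooled proportion, not a difference between arms. Nothing below depends on it.

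**2. Chance of an empty arm.** For a common rate p and n per arm, one arm is empty with probability q = (1−p)^n. A given active-versus-control pair contains an empty arm with probability 1−(1−q)². At least one of three arms is empty with probability 1−(1−q)³.

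| p | q, n=20 | given pair, n=20 | any of 3, n=20 | any of 3, n=18 |
|---|---|---|---|---|
| 5% | 36% | 59% | 74% | 78% |
| 10% | 12% | 23% | 32% | 39% |
| 15% | 3.9% | 7.6% | 11% | 15% |
| 20% | 1.2% | 2.3% | 3.4% | 5.3% |
| 50% | 0.0001% | 0.0002% | 0.0003% | 0.001% |

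Example at 10%, n=20: 0.90^20 = 0.1216, and 1−(0.8784)³ = 0.322. An empty arm somewhere is more likely than not only if p is below about 7.6% (n=20) or 8.4% (n=18).

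**3. What each method returns.** Take an illustrative table: control 0/20, MI 2/20, NRT 3/20.

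- *Ordinary logistic regression* does not converge. The log-odds ratios stop near 22.8 and 23.3, with standard errors near 60,000.
- *Chi-square and Cramer's V.* Expected events are 5/3 = 1.67 per arm and expected non-events 18.33. Chi-square = 4.667 × (1/1.667 + 1/18.33) = 3.05, p = 0.22, and V = √(3.05/60) = 0.23. Swapping the control and NRT counts leaves V unchanged, so V does not show which arm did better. As p = 0.22, the SAP's probing step would not be reached.
- *Risk difference with Newcombe interval.* The Wilson limits are 0 to 0.161 (0/20), 0.028 to 0.301 (2/20) and 0.052 to 0.360 (3/20). For MI, the lower limit is 0.10 − √(0.072² + 0.161²) = −0.08 and the upper limit is 0.10 + 0.201 = 0.30. For NRT, the lower limit is 0.15 − √(0.098² + 0.161²) = −0.04 and the upper limit is 0.15 + 0.210 = 0.36. Both are finite, signed and specific to an arm.

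**4. Small counts in the chi-square.** With 20 per arm, the expected event count is 20 × the overall rate, which is below 5 when that rate is under 25%. No exact test is named.

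**5. The missing-data rule.** Counting missing as smoking adds non-events for abstinence, so it cannot fill an empty arm.

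**The case against.** The strongest reply is that the later document drops logistic regression. The SAP uses chi-square for both of its dichotomous outcomes, and chi-square does not suffer separation. That stands. A reader might infer that separation threatens the current analysis of quit attempts and treatment contact, and the SAP does not support that reading. But the SAP's substitute does not provide the promised contrasts. It says that treatment versus control is the comparison of interest, yet it reaches that comparison only after a significant overall result, and it does not say how Dunnett's method applies to proportions.

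A reader might also infer that an empty arm is likely. The documents do not support that either. The only stated rate is 50%, for the main outcome, where the chance is about 3 in a million. Evidence on the other outcomes points both ways. Section 1.2 describes smokers who may not at first want cessation services. But participants volunteer for the study, every arm is referred to the quitline and the local program, and contact with either one counts.

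Finally, the protocol does not specify ordinary maximum likelihood and does not name the odds ratio. A penalised fit or a risk difference would be compatible with its wording, and arm counts, if published, let anyone calculate the difference. This shows that the remedy fits the plan. It does not show that the plan has chosen it.

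**Conclusion.** The point holds in a limited form. The protocol promises an arm-versus-control effect size for the yes/no outcomes, and no stated method is sure to deliver it. The SAP's gap does not depend on event rates: Cramer's V across three arms is unsigned and not a contrast, and contrasts depend on significance. The protocol's gap is conditional and confined to abstinence and, if it is uncommon, treatment seeking. At 20 per arm, the chance of at least one empty arm runs from about 74% at a 5% rate to 3% at 20%. These figures assume a common rate across arms and an ordinary maximum-likelihood fit. It would be wrong to say that an empty arm is probable, or to extend the risk to quit attempts.

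Abstinence is the most exposed outcome. It is a protocol outcome missing from the SAP's list, so the protocol's logistic model is the only analysis that names it.

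**What to change.** In the SAP, for each dichotomous outcome and including CO-verified abstinence, report the events and denominators by arm. Report also the risk difference of MI versus control and of NRT versus control, each with a Newcombe score interval, whether or not the three-group test is significant. Chi-square and Cramer's V can stay as secondary summaries.

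If an adjusted odds ratio is wanted for abstinence or treatment seeking, specify Firth-penalised logistic regression with profile-likelihood intervals, and do so before the analysis, not after a fit has failed. Such odds ratios will still be imprecise. In the illustrative table, adding 0.5 to each cell gives 5.5 (95% CI 0.25 to 123) for MI and 8.2 (0.40 to 170) for NRT. That is a reason to lead with the risk difference.

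The cost is a sentence or two in the SAP, a little more analysis work in standard software, and slight shrinkage of odds ratios toward 1 under Firth. No change to the design, sample size or data collection is needed.

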**B. Provide a power analysis. (As applicable, e.g. quantitative research).**

N/A. This is a small, pilot study. We will use the data collected in this study to estimate effect sizes for a larger NIH grant application.

**C. Describe the steps that will be taken to secure the data (e.g., training, authorization of access, password protection, encryption, physical controls, certificates of confidentiality, and separation of identifiers and data) during storage, use, and transmission.** The link between participants to their study ID will be stored in a password-protected file, located within a password-protected database on an encrypted computer. Only select trained laboratory personnel will have access to the file. All computer files or printed data used for analysis also

will be de-identified. Consent forms and payment forms will be stored in a locked file cabinet separate from data in an office (of Division of Addiction Psychiatry, [name]) that is locked when not occupied. All research personnel will complete CITI Human Subjects Research training and pass the CITI quizzes.

Additionally, we will obtain a Certificate of Confidentiality from the NIH

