### 1.2 Research Significance (*Briefly describe the following in 500 words or less*):

A disproportionate number of individuals who use tobacco are from low socioeconomic status (Tucker-Seeley et al., 2015). By reaching smokers at socioeconomic disadvantage who may not initially be interested in seeking cessation services and prompting quit attempts in this population, we can have a positive impact on public health.

Brief motivational interviewing is a psychosocial intervention designed to promote behavioral change and recommended as part of the clinical practice guidelines for smoking cessation (Fiore, 2008), in particular for populations with low motivation to quit. This intervention assumes clients are motivated and have the ability to quit. By avoiding direct advice or convincing, the therapist carefully uses a series of techniques to illicit intrinsic motivation from the client to change. Although MI presumably is designed to affect motivation, thereby eliciting behavioral change, mechanisms research does not support this relationship and instead suggest that a therapist's ability to engage the client in 'change talk,' i.e., talk about what it would look like to engage in different behaviors, is central to a favorable outcome. Whereas meta-analytic reviews of MI indicate relatively small effect sizes, a recent meta-analytic review that examined the combined effect of brief MI (i.e., <60 minutes) found that it was significantly related to long-term cessation ( $d=.33$ ). A similar significant effect for follow-up was found that MI that was not combined with pharmacotherapy ( $d=.21$ ).

Clinical practice guidelines additionally recommend the provision of NRT to enhance smoking cessation (Fiore et al., 2008) via reduction in nicotine withdrawal. Meta-analytic reviews generally provide support for the efficacy of NRT in promoting cessation, but are somewhat mixed. More recently, combination NRT is emerging as a preferred method that provides smokers with constant nicotine replacement (e.g., via the nicotine patch) as well as relief for 'breakthrough' cravings via the addition of gum or lozenge (Carpenter et al., 2013).

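### Effect sizes are meant for a larger application, but the SAP names only omnibus, unsigned measures without intervals, and 18–20 per arm leaves each contrast uncertain by about ±31 to 33 points

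*Protocol*

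**What the plan says.** Protocol section 1.5 sets the size: "We have a target N of 60 smokers (n=20/treatment condition". It names quit attempts as the main outcome and assumes a rate: "Estimating that 50% of the sample will make quit attempt during the course of the study, our main outcome of interest". It then says "this is adequate to group differences with 95% confidence (CI: 0.38, 0.61", which is the only precision figure in either document.

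Section 6.1 B answers the power-analysis prompt with "N/A. This is a small, pilot study" and continues: "We will use the data collected in this study to estimate effect sizes for a larger NIH grant application". Section 6.1 A states the contrast: "Because this is a small, pilot study, we will report effect sizes representing each of the two active interventions", each compared with referral only. It does not name the effect measure.

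The SAP names f for analysis of variance and Cramer's V for chi-square. Treatment-versus-control comparisons appear only as Dunnett follow-up of significant results. The SAP also refers to "handling data for the n=5 participants lost to follow-up". Neither document plans a confidence interval for an arm-versus-control effect, or says how the estimates would enter the design of a larger trial.

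**The concern.** There are two linked problems. First, the measures in the SAP are not the ones the protocol promises. f and Cramer's V each give a single number for the spread across three arms. They do not show which arm did better than control, or by how much, and they are above zero in almost every sample even when the arms do not differ.

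Second, even the right contrast is very imprecise with about 20 per arm. An interval would show this, but none is planned. A bare estimate passed to a grant application can look like a usable design effect. A favourable chance result would make the next trial too small. An unfavourable one could discourage a useful line of work or make the next trial needlessly large.

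**Working it through.** **The plan's own figure.** For p = 0.5 and n = 60, 0.5 ± 1.96·√(0.25/60) gives 0.373 to 0.627; the Wilson interval is 0.377 to 0.623. Neither gives both stated limits (0.38, 0.61). In any case this interval is for one overall proportion, not for a difference between arms.

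**Inputs.**
- Per-arm size: 60/3 = 20 (protocol 1.5). With the SAP's five losses, (60 − 5)/3 = 18.3. With the total of 64 in protocol 4.5, (64 − 5)/3 = 19.7. I used 18, 19 and 20.
- Rates: centred on the protocol's 50%.
- Next trial: two-sided 5% and 80% power, both assumed, because the documents state neither.
- True differences: 15, 25 and 30 points are assumed. About 9 points is converted from the d = .21 in protocol 1.2 for motivational interviewing without pharmacotherapy: odds ratio = exp(0.21·π/√3) = 1.46, which moves 50% to 1.46/2.46 = 59.4%.

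**Precision of one contrast.** Half-width = 1.96·√(2 × 0.25/n). At n = 20 this is 0.310 and at n = 18 it is 0.327, so ±31 to 33 points.

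**Needed size.** n per arm = (1.96 + 0.8416)²·(p₁q₁ + p₂q₂)/(p₁ − p₂)², where (1.96 + 0.8416)² = 7.849.
- 42.5% v 57.5%: 7.849 × 0.48875/0.0225 ≈ 170
- 45% v 54.4%: 7.849 × 0.4956/0.00884 ≈ 440
- 37.5% v 62.5%: 7.849 × 0.46875/0.0625 ≈ 59
- 35% v 65%: 7.849 × 0.455/0.09 ≈ 40

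**If the point estimate is used directly.** I enumerated every possible pair of binomial counts, put each pair of observed rates into the same formula, and compared the resulting plan with the needed size. Entries are percentages of all pilots at 18 / 19 / 20 per arm.

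| True difference | Plan at half the need or less | Estimate zero or negative | Plan at twice the need or more |
|---|---|---|---|
| 15 points | 40 / 42 / 32 | 23 / 22 / 21 | 11 / 21 / 22 |
| about 9 points | 40 / 41 / 42 | 34 / 34 / 33 | 13 / 12 / 12 |
| 25 points | 26 / 28 / 32 | 9 / 8 / 7 | 27 / 26 / 24 |
| 30 points | 24 / 27 / 24 | 5 / 4 / 4 | 21 / 27 / 27 |

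The percentages move unevenly with n because the counts are discrete, so a range is safer than any single value.

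**What half size means.** At half the needed n, power is Φ(2.8016/√2 − 1.96) = Φ(0.021), about 51% instead of 80%.

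**Check on a continuous scale.** With 18 to 20 per arm, the half-width on d is 0.62 to 0.65. A plan of half the need or less arises in 39–40% of pilots at d = 0.21, 34–35% at d = 0.33 (the other value in protocol 1.2), 26–28% at d = 0.5 and 16–18% at d = 0.8.

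**Cramer's V with no true difference.** In simulation with all three arms at 50%, V averages 0.17 at 18 per arm and 0.16 at 20.

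**The case against.** The strongest reply is that the protocol never says the point estimate will be used as the design effect. An application can show pilot results as preliminary evidence and base its power on something else. That stands: every sizing percentage above depends on direct use, which is my assumption.

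The true effects are also assumed. The 15-point figure has no source in the documents. The d = .21 concerns motivational interviewing and cessation at follow-up, not NRT sampling or one-month quit attempts. Undersizing becomes less frequent as the true effect grows, and the error also runs towards oversizing. All of this stands and is why ranges are given.

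The plan calls itself a small pilot and claims no power. The logistic models in protocol 6.1 A could also supply odds ratios with intervals. But neither document commits to reporting them, and the SAP uses chi-square for its binary outcomes.

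A reader might go further and infer that feeding the application is the only use of the data, or that the trial's purpose is therefore not met. The documents do not support either. Protocol 1.1 states the purpose as examining strategies to encourage quitting, with a direct comparison of three conditions and superiority hypotheses. Section 6.4 plans presentation and publication. The SAP wants effect sizes to show which aspects of the pilot may be most beneficial. The larger application is one use among several.

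**Conclusion.** The point holds as a gap in reporting and planned use. The protocol promises active-versus-control effects and intends effect sizes for a larger application. The SAP specifies measures without direction, arm or interval. The ±31 to 33 points rests only on the planned arm sizes and rates near 50%.

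The sizing risk is conditional on direct use of the point estimate. At half the need or less, it is about 32–42% of pilots at 15 points, 40–42% at about 9 points, and 24–32% at 25 to 30 points. At 15 and 9 points, the estimate is zero or negative in 21–23% and 33–34% of pilots, and 11–22% of pilots would lead to a plan of twice the need or more.

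It would be too strong to say that the next trial will be undersized, because the documents do not say how it will be sized. Nothing here affects the validity of this trial's own comparisons.

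**What to change.** In protocol 6.1 A and the SAP, report each active-versus-control effect with its 95% confidence interval, alongside or in place of f and Cramer's V. Use a risk difference or odds ratio for binary outcomes and an adjusted mean difference for continuous ones. Do this whether or not the omnibus test is significant, and state whether the intervals are unadjusted or Dunnett simultaneous.

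In protocol 6.1 B, replace the sentence on effect sizes with wording such as:

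> The pilot will inform the control-arm rate, standard deviations, baseline-to-follow-up correlation, retention and enrolment rate for a larger trial. Arm-versus-control estimates will be presented with their 95% confidence intervals and will not be used alone as the design effect. The larger trial will be sized on a pre-stated worthwhile difference.

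This leaves the investigators free to show the pilot estimates in the application. It needs no extra participants, visits or data, only changed wording and a few more lines of output. The cost is that the effect will look less persuasive beside its interval, and a worthwhile difference has to be agreed and justified.
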